### **Bone Mineral Density**

*Measurements of Bone Mineral Density (BMD) will be performed for all patients at 6 and 12 months to assess potential steroid-related changes. Results of BMD, including investigator’s interpretation, are recorded on the ‘Bone Mineral Density’ eCRF page.*

### **Tanner Staging**

*Assessment of physical development, sexual maturation, and the effect of treatment with dexamethasone on these aspects will be evaluated using the Tanner scale at 6 and 12 months. The scale defines physical measurements of development in children, adolescents and adults based on external primary and secondary sex characteristics, such as the size of the breast, genitals, testicular volume and development of pubic hair. Due to natural variation, individuals pass through the Tanner stages at different rates, depending in particular on the timing of puberty. Tanner staging of the breasts in pre-menarchal females and of the scrotum in males who have not completed puberty, will be performed. Post-menarchal females and males who have completed puberty will be excluded from this growth analysis.*

Results of Tanner Staging assessments are recorded on the 'Tanner Scale' eCRF page.

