Study treatment administration by IV infusion, will be performed within 30 min after the EDS process has been completed.

The satellite sample bag will be detached and used for sterility culture tests: a sample of the EDS-EP (approximately 1 ml per inoculum for a total of 2 mL) will be collected to perform a sterility test using a culture-based method as presented in [Appendix 10](#). A 1-mL sterile sample of the EDS-EP will be stored under refrigeration as a "Retention Sample". In case of positive/contaminated post-release sterility results, an action plan has been established as presented in [Section 13.6](#) and in [Appendix 11](#).

After completion of the IV infusion of the study treatment the following assessments will be performed: Vital signs, physical examination (1-2 hr after infusion), assessment of AEs, and assessment of concomitant medications

*Months 6 and 12*

At Months 6 and 12 the following assessments will be performed before treatment administration: all assessments of efficacy (ICARS, CGI-C, CGI-S and EQ-5D-5L) and safety (vital signs, ECG, routine laboratory tests on the diverted blood samples (see [Section 11.5](#)), physical and neurological examinations, C-SSRS, BMD and assessments of AEs and concomitant medication use), as well as special laboratory tests (HbA1c, CD4+ lymphocytes count and CRP), on the diverted blood samples (see [Section 11.5](#)). A serum (on the diverted blood samples, see [Section 11.5](#)) and urine pregnancy test will be performed for women of childbearing potential. Physical development, sexual maturation, and the effect of treatment with dexamethasone on these aspects will be assessed (Tanner scale). Tanner staging of the breasts in pre-menarchal females and of the scrotum in males who have not completed puberty, will be performed at Months 6 and 12. Post-menarchal females and males who have completed puberty will be excluded from this growth analysis.

CCI  
[Redacted]

Study treatment administration by IV infusion, will be performed within 30 min after the EDS process has been completed.

CCI  
[Redacted]

After completion of the IV infusion of the study treatment, a physical examination and vital signs will be performed (1-2 hr after infusion), as well as assessments of AEs and concomitant medication use.

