## 11.4 Visit Schedule and Assessments

### 11.4.1 Screening phase (D -30 to -1)

Applicable only for patients which will be enrolled without completing the ATTeST trial.

After providing consent/assent, as described in [Section 11.1](#), patients will enter the screening phase. The screening phase will last at maximum 30 days. Any previous treatments with corticosteroid compounds will be withdrawn (washout from previous treatment), while for other patients the screening phase may coincide with the screening visit (1 day long, provided that all the required laboratory reports are available and reviewed before the eligibility confirmation at the baseline). As soon as all screening assessments/procedures have been performed and eligibility is confirmed, the patients can undergo the baseline visit.

The following screening evaluations will be conducted:

- a) Medical history and demographics
- b) Physical examination
- c) Vital signs (including height and weight in triplicate)
- d) Neurological examination
- e) Tanner staging of the breasts in pre-menarchal females and of the scrotum in males who have not completed puberty. Post-menarchal females and males who have completed puberty will be excluded from this growth analysis.
- f) ICARS (administered by the qualified site-specific rater).
- g) CGI-S
- h) 12-lead standard Electrocardiogram (ECG)
- i) Routine laboratory tests, on the diverted blood sample (see [Section 11.5](#))
- j) Special laboratory tests: HbA1c, CD4+ lymphocytes count, and CRP, on the diverted blood sample (see [Section 11.5](#))
- k) Serum pregnancy test (women of childbearing potential), on the diverted blood sample (see [Section 11.5](#))
- l) BMD
- m) CSSRS
- n) EQ-5D-5L
- o) Blood collected to assess RBC osmotic resistance (in selected centers)

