## 8. Analysis Methods

### 8.1 General Methods

For continuous variables, the mean, standard deviation (SD), minimum, median and maximum as well as 1st and 3rd quartile (Q1, Q3) are presented, together with the total number of observations and the number of non-missing values. Unless otherwise specified minimum and maximum values are reported to the same number of decimal places as the recorded measurements, mean, median, 1st and 3rd quartile are reported to one more decimal place and standard deviation one additional decimal place more than the mean.

For categorical variables, absolute and relative frequencies are reported. Relative frequencies are based on all observations and reported as a percentage to one decimal place. Unless otherwise specified percentages are based on the number of patients with data and are not calculated for missing categories.

Adverse events, medical histories and concomitant medications are reported on a patient basis, i.e. if a patient reported several events coded to the same coding term the patient is counted only once at the respective level of display. The percentages are calculated using the number of patients in the population Analysis Set as the denominator.

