### 10.1 Disposition of Patients

A listing presents study completion data, including the primary reason for study discontinuation, for the Total Set (TOT).

A table summarizes the disposition of patients in the Total Set. This includes a summary of the number of patients who completed the study, the number of patients who had a treatment interruption due to COVID-19, the number of patients who discontinued the study, and the primary reason for discontinuation.

The number of patients who attended Scheduled Visits is summarized (Visit Attendance) by absolute counts (n) and percentages (%) for the SAF.

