### 10.7.3 Pregnancy Testing

Results of serum and urine pregnancy tests are listed for the SAF.

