#### **10.7.11 Tanner Staging**

All recorded Tanner Staging data are included in a listing for the SAF.

The absolute counts (n) and percentage (%) of patients at each Tanner stage is summarized by visit for the SAF.

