### Laboratory Values

|                  |   |     |   |
|------------------|---|-----|---|
| Table 14.3.2-1.1 | Summary of Hematology Laboratory Parameters         | SAF | U |
| Table 14.3.2-1.2 | Summary of Clinical Chemistry Laboratory Parameters | SAF | R |
| Table 14.3.2-1.3 | Summary of Special Laboratory Parameters            | SAF | R |
| Table 14.3.2-1.4 | Summary of Urinalysis Laboratory Parameters         | SAF | U |

|                     |  |     |   |
|---------------------|--|-----|---|
| Table 14.3.2-2.1    | Summary of Clinically Notable Hematology Laboratory Parameters         | SAF | U |
| Table 14.3.2-2.2    | Summary of Clinically Notable Clinical Chemistry Laboratory Parameters | SAF | R |
| Table 14.3.2-2.3    | Summary of Clinically Notable Urinalysis Laboratory Parameters         | SAF | R |
| Table 14.3.2-3.1    | Summary of Shift in Special Laboratory Parameters from Baseline        | SAF | U |
| Other Safety |  |     |   |
| Table 14.3.3-1.1    | Summary of Culture-Based Sterility Test                                | SAF | U |
| Table 14.3.-1.2     | Summary of Process Events  | SAF | U |
| Table 14.3.3-2.1    | Summary of Vital Sign Data   | SAF | U |
| Table 14.3.3-2.2    | Summary of Clinically Notable Change from Baseline Vital Signs         | SAF | U |
| Table 14.3.3-3.1    | Summary of Physical Examination Data                                   | SAF | U |
| Table 14.3.3-3.2    | Summary of Neurological Examination Data                               | SAF | R |
| Table 14.3.3-4      | Summary of ECG Data  | SAF | U |
| Table 14.3.3-5.1    | Summary of Columbia-Suicide Severity Rating Scale (C-SSRS) Children's  | SAF | U |
| Table 14.3.3-5.1    | Summary of Columbia-Suicide Severity Rating Scale (C-SSRS) Adult's     | SAF | R |
| Table 14.3.3-6.1    | Summary of Bone Mineral Density z-scores                               | SAF | U |
| Table 14.3.3-6.2    | Summary of Shift in Bone Mineral Density z-scores from Baseline        | SAF | U |
| Table 14.3.3-7.1    | Summary of Tanner Staging data   | SAF | U |

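### The Tanner table does not say when pubertal status is judged, and on the likelier reading patients who mature drop out of it uncounted (minor).

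*SAP*

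**What the plan says.** SAP 7.4.8 (Tanner Staging) and Protocol 13.9 give the purpose as evaluating physical development, sexual maturation and the effect of dexamethasone on them. Staging uses breasts in girls and scrotum in boys, and only in those not yet mature. The SAP adds: "Post-menarchal females and males who have completed puberty will be excluded from this growth analysis".

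The restriction appears at more than one time point. Protocol 11.4.1 has it at screening: "Tanner staging of the breasts in pre-menarchal females and of the scrotum in males who have not completed puberty". Protocol 11.2, under Months 6 and 12, has it again: "of the scrotum in males who have not completed puberty, will be performed at Months 6 and 12". Neither document says whether status is settled once or re-judged at each assessment.

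The analysis in SAP 10.7.11 is a listing of the recorded data plus one table: "The absolute counts (n) and percentage (%) of patients at each Tanner stage is summarized by visit for the SAF". SAP 12.1 confirms a single output, Table 14.3.3-7.1, "Summary of Tanner Staging data". On denominators, SAP 8.1 says: "Unless otherwise specified percentages are based on the number of patients with data and are not calculated for missing categories". SAP 8.2.1.2 refers missing data back to section 7, which has no rule for Tanner staging.

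**The concern.** The exclusion rule depends on the outcome that the table is meant to describe. A girl who reaches menarche or a boy who completes puberty has progressed, and that progress takes the patient out of the staged group. No planned output counts these patients.

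Two further features make the table hard to read. Breast and scrotal stages are pooled, because no split by sex is specified. There is also no comparison with the patient's own baseline stage. The SAP handles similar matters more fully elsewhere: for the C-SSRS it fixes the choice of version by age at the baseline visit (SAP 7.4.8), and for bone mineral density it plans change from baseline and a shift table (SAP 10.7.10).

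At stake is a descriptive safety output in a mainly paediatric study of a steroid. A falling n would mix maturation with dropout and missed assessments. The share at low stages would be higher than in the cohort that started.

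**Working it through.** The plan states no figure to reproduce, so the check is a comparison of texts followed by arithmetic on the denominator.

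**1. When status is judged.** The rule is attached to screening and again to Months 6 and 12. Strictly, the Months 6 and 12 wording dates the examination, not the judgement of status. A per-visit judgement is the likelier reading but not the only one. Fixing status at baseline for the analysis alone would not fully cure the problem, because staging itself is done only in patients not yet mature. A girl who was pre-menarchal at baseline would have no stage recorded after menarche.

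**2. Denominator.** SAP 8.1 bases percentages on patients with data unless otherwise specified. The sentence before it bases relative frequencies on all observations, which does not sit well with that. Table shells are not provided. Patients with data is therefore the probable denominator, not a certain one.

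**3. Exact effect if both readings hold.** Let N patients be eligible at baseline and still on study, L of them no longer staged because they matured, and n_k at stage k. Set q = L/N.

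- Planned percentage: n_k/(N - L)
- Percentage of the eligible cohort: n_k/N
- Ratio: N/(N - L) = 1/(1 - q)

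q = 10% gives 1/0.90 = 1.11; q = 25% gives 1/0.75 = 1.33; q = 45% gives 1/0.55 = 1.82.

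**4. Direction, with assumed counts.** Take 30 patients staged at baseline, with 12/6/6/6/0 at stages 1 to 5. Some of the six at stage 4 mature and nobody else changes.

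| Matured | Denominator | Stage 4-5, planned | Stage 1, planned |
|---|---|---|---|
| 0 | 30 | 6/30 = 20.0% | 12/30 = 40.0% |
| 2 | 28 | 4/28 = 14.3% | 12/28 = 42.9% |
| 4 | 26 | 2/26 = 7.7% | 12/26 = 46.2% |
| 6 | 24 | 0/24 = 0.0% | 12/24 = 50.0% |

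With all 30 kept and a row for those who matured, stage 4-5 or matured stays at 6/30 = 20.0% and stage 1 stays at 40.0%.

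**5. Size, illustration only.** The documents give no ages at menarche or at each stage, so q was simulated under assumptions, with no dropout:

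- Baseline age: normal, mean 11.2 and SD 3.5 (the 22-patient pilot, Protocol 7.1.3.1), cut off below age 6. The cut-off raises the simulated mean to about 11.7. The mean parameter was varied from 10.2 to 12.2.
- Girls: stages 2 to 5 at mean ages 10.0/11.3/12.3/14.0; menarche at 12.8, varied from 12.3 to 13.5.
- Boys: stages 2 to 5 at 11.0/12.5/13.5/15.0, leaving on reaching stage 5.
- Shared timing SD 1.1 years (0.8 to 1.4), milestone SD 0.4 years, and a delay of 0 to 2 years, since Protocol 7.3 lists delayed organ maturation among the features of the disease.

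| | q, central case | q, range | 1/(1-q), range |
|---|---|---|---|
| Girls, Month 12 | 17% | 6-23% | 1.06-1.30 |
| Girls, Month 24 | 35% | 14-44% | 1.16-1.79 |
| Boys, Month 12 | 9% | 3-12% | 1.03-1.14 |
| Boys, Month 24 | 21% | 7-26% | 1.08-1.35 |

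Neither document defines completed puberty. If a boy's stage 5 is recorded once before staging stops, the central values for boys fall to 4% and 15%. Month 24 concerns only patients who continue past the planned 12 months.

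**6. Muted, not reversed.** In the central case the planned share of girls at stage 1 still falls over time: 51% at baseline, 46% at Month 6, 42% at Month 12 and 32% at Month 24. The eligible-cohort share at Months 12 and 24 is 35% and 21%. The table shows progress, but too little of it.

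**The case against.** The strongest reply is that the harm needs two unsettled readings at once. If percentages are taken over all patients, the factor 1/(1-q) does not arise. That is correct. Even then no row would identify those who matured, and a general missing row would pool them with missed assessments and dropouts.

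A second reply is that other outputs help. Tanner data are listed by patient. SAP 10.1 plans attendance: "The number of patients who attended Scheduled Visits is summarized (Visit Attendance) by absolute counts (n) and percentages (%) for the SAF". SAP 10.7.3 adds: "Results of serum and urine pregnancy tests are listed for the SAF". The pregnancy-test listing is an indirect marker of menarche. Height is measured, and stunted growth is an adverse event of special interest. This stands in part: an individual course can be traced by hand until staging stops. None of these counts girls who reached menarche, and the pregnancy tests say nothing about boys. Height concerns growth rather than sexual maturation.

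A third reply is that Tanner stage drives no decision and that a shift table and a split by sex are refinements. Protocol 13 does list Tanner staging among the safety assessments, but SAP 3.4 does not name it among the components of the primary endpoint. This limits the weight of the point.

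A reader might infer that the table would show false pubertal delay caused by treatment, or would conceal a real slowing by a calculable amount. The documents support neither. The distribution still moves upward, every patient receives EDS-EP, there is no comparator with normal tempo, and no version of this table isolates a drug effect.

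**Conclusion.** The point holds, at minor weight. The reference time for pubertal status is missing, stage by visit is the only tabulation, and no output counts patients who mature; all three follow directly from the text. The shift toward lower stages, relative to the cohort eligible at baseline, also needs per-visit status (likelier) and the patients-with-data denominator (probable). Given both, the factor 1/(1-q) is exact. The value of q is not in the documents. The simulated values rest wholly on outside puberty timings and an assumed exit rule for boys, so they show only that the effect could be noticeable. It would be wrong to read them as estimates for this trial, or to read the gap as damage to the primary safety endpoint.

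**What to change.** Amend SAP 7.4.8 and 10.7.11:

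1. Define the Tanner set by status at OLE-IEDAT baseline: pre-menarchal females, and males who have not completed puberty.
2. At each 6-monthly visit keep these patients in the denominator while they are on study. Add two rows: *menarche reached / puberty completed* and *not staged, reason unknown*.
3. Add a shift table from baseline stage to each visit, by sex. Show the total column only, because sex by seven ATTeST groups would be sparse with at most 150 patients.

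The cost is some SAP wording, one derived category and one extra table, with no new procedure. Some patients, mainly boys, may fall in *reason unknown* if the eCRF does not record why staging stopped, which the documents do not confirm. For girls, the menstrual status behind the pregnancy testing in Protocol 14.4 can serve as a proxy. The revised table gives the proportion reaching menarche or completing puberty, not the stage after that.

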**7.4.9 Pharmacokinetic Variables**

Not applicable.

**7.4.10 Pharmacodynamic Variables**

Not applicable.

**7.4.11 Pharmacoeconomic Variables**

Not applicable.

## 8. Analysis Methods

### 8.1 General Methods

For continuous variables, the mean, standard deviation (SD), minimum, median and maximum as well as 1st and 3rd quartile (Q1, Q3) are presented, together with the total number of observations and the number of non-missing values. Unless otherwise specified minimum and maximum values are reported to the same number of decimal places as the recorded measurements, mean, median, 1st and 3rd quartile are reported to one more decimal place and standard deviation one additional decimal place more than the mean.

For categorical variables, absolute and relative frequencies are reported. Relative frequencies are based on all observations and reported as a percentage to one decimal place. Unless otherwise specified percentages are based on the number of patients with data and are not calculated for missing categories.

Adverse events, medical histories and concomitant medications are reported on a patient basis, i.e. if a patient reported several events coded to the same coding term the patient is counted only once at the respective level of display. The percentages are calculated using the number of patients in the population Analysis Set as the denominator.

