### 3.6 Changes in the Conduct of Study or Planned Analysis compared to protocol

According to section 16.2.1 of the protocol the safety analysis set should be defined as follows:

*Safety Population (SP): All subjects who receive a dose of study medication and have at least one post-dose safety assessment will be included in the safety analyses.*

However, to be in line with general guidance like ICH E9 it was decided to include all patients who received any dose of study medication during this OLE-IEDAT study into the safety analysis set, regardless of the presence of post-dose safety assessments.

The schedule of events in Section 3.3 of this SAP is a copy from the protocol apart from one difference: To clarify that in this SAP also uses baseline from the ATTeST study the column “Baseline” has been renamed to “OLE-IEDAT Baseline”.

Section 16.2.6 of the protocol states: *Additional analyses will be performed to determine the change in each of the efficacy measures compared to the baseline of the IEDAT-02-2015 study, comparing patients who were treated with EDS-EP throughout the double-blind and open-label treatment periods vs. those who received placebo for varying periods in Study IEDAT-02-2015, before being switched to the active treatment.*

However, as described in Section 6.3 of this SAP this comparison will not be limited to efficacy or the protocol defined groups and all summaries in this study will display the 7 treatment groups from the ATTeST study. Subgroups for Age (<10 years, ≥ 10 years) and Region (India; Europe, Australia, Tunisia; United States) are also included.

Section 12.1.1 of the protocol outlines the ICARS assessment, including a description of the “Modified” ICARS (mICARS). As described in Section 3.4 of this SAP, the “Rescored” mICARS is also considered as an endpoint in the analysis.

A definition of continuous exposure is added to Section 7.1 to support future analysis.

Visit periods of 12 months is assessed to Section 7.1 and these are used in summary of Adverse Events described in Section 10.7.1. To investigate Adverse Events by the period in which they occur.

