### 5.3 SAS-Programming Quality Level

The following quality level of programming deliverables is applied, as per contract with EryDel. All statistical output receives a tailored Quality Control (QC) approach by:

| Deliverable  | Double Programming? |
|--|---------------------|
| CDISC SDTM datasets   |                     |
| Including QC against the applicable CDISC guidelines.                    | YES                 |
| CDISC ADaM datasets   |                     |
| Including QC against the SAP and applicable CDISC guidelines.            | YES                 |
| Tables and Figures (including in-text tables and in-text figures) | YES                 |
| Inferential analyses  | YES                 |

| Listings   |     |
|---|-----|
| ○ Listings for Data Review Meeting that do not need complex selection     | NO  |
| ○ Listings for Data Review Meeting that do need complex selection*        | YES |
| * The selection of the data is double programmed from the source dataset. |     |

All TLFs undergo the following by the Quality Control (QC) team:

- Comparison with specifications (i.e., SAP and shells)
- Cross checking with other TLFs for consistency and correctness
- Sensibility review
- SAS log review
- In addition, a Principal/Senior Statistician or the Head of Programming and Biostatistics Unit (independent of the study team) performs a senior review of all data and TLFs to pre-empt customer comments allowing points of interest to be highlighted and discussed at EryDel handover.

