### 6.3 Subgroup Definitions

Patients are grouped by their treatment group in the ATTeST study: EDS-EP Low Dose, EDS-EP High Dose, Non-switch Placebo, Visit 9 Low Dose, Visit 9 High Dose, Visit 12 EDS-EP Low Dose, and Visit 12 High Dose. All outputs contain columns to display these groups.

The following endpoints are also summarised by subgroups for Age (<10; ≥10 years) and Region (India; Europe, Australia, and Tunisia; United States):

- ICARS
- mICARS
- RmICARS
- CGI-C
- CGI-S
- EQ-5D-5L

Patients with a treatment gap of greater than 76 days between the ATTeST study and the OLE-IEDAT study are presented as a separate subgroup for outputs as outlined in Section 10.

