### Intervals from First OLE-IEDAT Infusion

Adverse Event analysis outlined in Section 10.7.1 is displayed overall and in 12 month intervals from first OLE-IEDAT Infusion.

These are derived by calculating day since First OLE-IEDAT Infusion:

$$\text{Day since First OLE-IEDAT Infusion} = (\text{Date of event} - \text{Date of First OLE-IEDAT Infusion})$$

This is then mapped to 12 months intervals as follows:

| Interval        | Window              |
|-----------------|---------------------|
| 0 to 12 months  | Day in [0, 364]     |
| 12 to 24 months | Day in [365, 729]   |
| 24 to 36 months | Day in [730, 1094]  |
| 36 to 48 months | Day in [1095, 1459] |
| 48 to 62 months | Day in [1460, 1824] |
| ...             | ...                 |

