## 10. Overview of Tables, Listings and Figures

Unless otherwise stated summary tables are produced based on the complete analysis set mention in the respective section. The treatment groups from the ATTeST study are presented on all outputs.

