## 10.7 Safety Results

### 10.7.1 Adverse Events

#### Brief Summary of Adverse Events

An overview of AEs (including the number of patients with at least one TEAE, at least one TESAE, at least one TEAE leading to Death, at least one AESI, the number of patients who permanently withdrew the Study Treatment due to a TEAE, AEs during COVID-19 interruption, the worst intensity of any TEAE experienced by each patient with at least one TEAE and the closest relationship to Study Treatment of any TEAE experienced by each patient with at least one TEAE) is summarized for the SAF.

This summary is repeated for each 12-month period as described in Section 7.1.

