### Adverse Events

|                    |   |     |   |
|--------------------|---|-----|---|
| Table 14.3.1-1.1.1 | Summary of Adverse Events   | SAF | U |
| Table 14.3.1-1.1.2 | Summary of Adverse Events by 12 Month Period  | SAF | U |
| Table 14.3.1-1.2   | Treatment Emergent Adverse Events by System Organ Class and Preferred Term  | SAF | U |
| Table 14.3.1-1.3   | Treatment Related Treatment Emergent Adverse Events by System Organ Class and Preferred Term                              | SAF | R |
| Table 14.3.1-1.4   | Adverse Events of Special Interest by System Organ Class and Preferred Term   | SAF | R |
| Table 14.3.1-1.5   | Treatment Emergent Adverse Events by Worst Intensity by System Organ Class and Preferred Term                             | SAF | R |
| Table 14.3.1-1.6   | Treatment Emergent Adverse Events Leading to Death by System Organ Class and Preferred Term                               | SAF | R |
| Table 14.3.1-1.7   | Treatment Emergent Serious Adverse Events by System Organ Class and Preferred Term  | SAF | R |
| Table 14.3.1-1.8   | Treatment Emergent Adverse Events That Led to Discontinuation of Study Treatment by System Organ Class and Preferred Term | SAF | R |
| Table 14.3.1-1.9   | On Dose Treatment Emergent Adverse Events During COVID-19 Treatment Interruption by System Organ Class and Preferred Term | SAF | R |
| Table 14.3.1-1.10  | Off Dose Adverse Events During COVID-19 Treatment Interruption by System Organ Class and Preferred Term                   | SAF | R |
| Table 14.3.1-1.11  | Restart Treatment Emergent Adverse Events After COVID-19 Treatment Interruption by System Organ Class and Preferred Term  | SAF | R |

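### The by-period adverse event table divides by the full Safety Analysis Set, so percentages in later 12-month periods read too low

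*SAP*

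**What the plan says.** SAP 8.1 gives AEs their own denominator rule: "The percentages are calculated using the number of patients in the population Analysis Set as the denominator". The AE display text in SAP 10.7.1 repeats it, basing percentages on the patients in the population. SAP 10 adds a default: "Unless otherwise stated summary tables are produced based on the complete analysis set mention in the respective section".

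The AE overview in SAP 10.7.1 is defined for the SAF and then extended in one sentence: "This summary is repeated for each 12-month period as described in Section 7.1". SAP 12.1 lists the result as Table 14.3.1-1.1.2, "Summary of Adverse Events by 12 Month Period", population SAF.

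SAP 7.1 supplies the periods: "Adverse Event analysis outlined in Section 10.7.1 is displayed overall and in 12 month intervals from first OLE-IEDAT Infusion". It assigns event dates to 365-day windows and does not say which patients are at risk in a window. SAP 3.6 gives the reason for adding the periods: "To investigate Adverse Events by the period in which they occur". SAP 6.3 splits outputs by ATTeST treatment group: "All outputs contain columns to display these groups".

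Neither document contains a period-specific denominator, person-time, or an exposure-adjusted AE rate.

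**The concern.** One OLE infusion puts a patient in the SAF for good (SAP 6.1), but patients are followed for very different lengths of time:

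- The Protocol Synopsis plans entry from 12 June 2018 to the third quarter of 2021.
- Treatment is planned for 12 months and may be extended with no fixed end.
- SAP 7.4.1 records that Indian sites were terminated because of COVID-19. It also records that patients noted as completers in Italy and the USA left when the study was terminated.

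Under the stated rule, a patient no longer observed still sits in the denominator of every later period and cannot contribute an event. If retention differs between ATTeST groups, the columns are also diluted to different degrees.

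Long-term safety is the primary objective, and this is the only listed AE table by period since first OLE infusion. Its purpose is to show when events occur. With this denominator it partly shows when patients left, and the error runs in the favourable direction.

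**Working it through.** The plan states no AE percentage, retention or sample size calculation, so it has no figure of its own to reproduce. The check is the arithmetic of the rule, followed by illustrations.

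**Rule.** Let x_k be the patients with an event in period k, N the SAF size (or the SAF size of a column), and R_k the patients still under observation at the start of period k.

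- As written: x_k / N.
- Among patients entering the period: x_k / R_k.
- Hence the printed % = (x_k / R_k) × (R_k / N). The two agree only if R_k = N.

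Example with the protocol's maximum of 150 patients, 60 of them still observed (assumed) and 36 with an event (assumed): 36/60 = 60%, but the table prints 36/150 = 24%.

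**Illustration (a): constant 60% annual risk, with dropout.** Risk and loss are assumptions. The event hazard is h = −ln(0.4) = 0.916 per year. Let r be annual retention and d = −ln(r).

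- Loss at anniversaries: 60 × r^(k−1).
- Continuous loss: 100 × r^(k−1) × h/(h+d) × (1 − exp(−(h+d))).

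| Annual loss, timing | Year 1 | 2 | 3 | 4 | 5 |
|---|---|---|---|---|---|
| 20%, anniversaries | 60.0 | 48.0 | 38.4 | 30.7 | 24.6 |
| 10%, continuous | 57.4 | 51.7 | 46.5 | 41.8 | 37.7 |
| 20%, continuous | 54.7 | 43.7 | 35.0 | 28.0 | 22.4 |
| 40%, continuous | 48.8 | 29.3 | 17.6 | 10.5 | 6.3 |

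Under either timing, the fall relative to year 1 is r^(k−1).

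**Illustration (b): a true rise.** Assumed annual risks of 40, 45, 50, 55 and 60% with 20% annual loss print as 40.0, 36.0, 32.0, 28.2 and 24.6% (anniversaries), or 36.2, 32.6, 29.0, 25.6 and 22.4% (continuous).

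**Illustration (c): no dropout, staggered entry only.** From 12 June 2018 to 1 July 2021 is 1115 days (3.05 years); to 30 September 2021 it is 1206 days (3.30 years). Only these planned entry dates come from the documents. Assume uniform entry over E years and a common stop T years after first subject in. The share reaching the start of year k is min(1, (T−k+1)/E). The printed % averages 1 − exp(−0.916 × time observed in the period) over entry times.

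| T = 5 years | Year 1 | 2 | 3 | 4 | 5 |
|---|---|---|---|---|---|
| Reach period start, E = 3.05 | 100 | 100 | 98.3 | 65.5 | 32.8 |
| Reach period start, E = 3.30 | 100 | 100 | 90.9 | 60.6 | 30.3 |
| Printed %, E = 3.05 | 60.0 | 60.0 | 50.6 | 31.0 | 11.3 |
| Printed %, E = 3.30 | 60.0 | 59.4 | 46.8 | 28.6 | 10.5 |

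With T = 6 the printed series is 60.0, 60.0, 60.0, 50.6, 31.0 (E = 3.05) or 60.0, 60.0, 59.4, 46.8, 28.6 (E = 3.30).

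**Is a start-of-period N enough?** Not quite. In (c) with T = 5, dividing by R_k still gives about 60, 59–60, 52, 47 and 35%, because some patients are observed for only part of a period. The first-event rate stays at 91.6 per 100 patient-years at risk in every period.

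**The case against.** The strongest reply is that the percentages in this table are inferred. The overview text in SAP 10.7.1 speaks of numbers of patients, the percentage rule comes from 8.1, and the table shells are not among the documents. SAP 5.3 checks outputs against both SAP and shells, so the shells could carry period Ns. That is possible. If they do, they conflict with the SAP text, which still needs correcting.

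A second reply is that x_k / N is a legitimate quantity: the share of all treated patients with an event in that period. That is true, but it does not serve the purpose stated in SAP 3.6, and nothing warns the reader to take it that way.

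Third, visit attendance (SAP 10.1) and exposure (10.5) are tabulated, so a reader could roughly rescale. They are not linked to this table.

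The general categorical rule in 8.1, which uses patients with data, does not help. It yields where something else is specified, and the AE sentence specifies something else.

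Three limits stand. The size is hypothetical. Counts and the overall AE tables do not have this by-period dilution. A start-of-period N alone does not remove the whole effect.

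**Conclusion.** The concern holds. Read as written, SAP 8.1, 10 and 10.7.1 divide every period of Table 14.3.1-1.1.2 by the full SAF, or by the full SAF count of each ATTeST column. Later percentages are then too low as a description of risk among patients still observed, by the factor R_k/N. The direction follows from the text and the documented unequal follow-up. The actual size cannot be determined from the documents, and every illustrated figure rests on assumed risk, retention, entry pattern and stop date.

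This should be fixed, but its reach is limited to one descriptive table. It concerns how the primary safety objective reads over time and touches no test. The remaining uncertainty is what the shells show.

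**What to change.** 1. In SAP 8.1 and 10.7.1, state that the denominator for the by-period AE summary is the number of SAF patients, per column, still under AE observation at the start of the period. Print that N in the header.
2. Add patients with a first event in the period per 100 patient-years at risk in that period, counting time up to that first event.
3. Define observation as running from first OLE infusion to the later of 30 days after the patient's actual final visit and 60 days after the final infusion, or to earlier death, loss to follow-up or data cut-off. Count only events within that time. SAP 7.4.8 now ties the final visit to Month 12 or early discontinuation, which does not describe patients treated longer, although its 60-day limb still gives them an end date.
4. State which events enter the table. SAP 7.4.8 calls all OLE adverse events treatment-emergent, but its COVID-19 interruption text excludes, for patients with long gaps, events more than 60 days after the last dose. These must be reconciled so that numerator and observation time match.
5. Align the shells.

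The cost is SAP and shell wording, one derived observation-time variable per patient and period, header Ns and a few table rows. Later-period percentages will look less favourable.
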